### 5.2.1.2.2 Pembrolizumab

Adverse events (both non-serious and serious) associated with pembrolizumab exposure may represent an immunologic etiology. These immune-related adverse events (irAEs) may occur shortly after the first dose or several months after the last dose of pembrolizumab treatment and may affect more than one body system simultaneously. Therefore, early recognition and initiation of treatment is critical to reduce complications. Based on existing clinical trial data, most irAEs were reversible and could be managed with interruptions of pembrolizumab, administration of corticosteroids, and/or other supportive care. For suspected irAEs, ensure adequate evaluation to confirm etiology or exclude other causes. Additional procedures or tests such as bronchoscopy, endoscopy, or skin biopsy may be included as part of the evaluation. Based on the severity of irAEs, withhold or permanently discontinue pembrolizumab and administer corticosteroids. Dose modification and toxicity management guidelines for irAEs associated with pembrolizumab are provided as per [Table 1](#) below.

**Table 1. Dose Modifications and Toxicity Management Guidelines for Immune-related AEs Associated with Pembrolizumab**

General instructions:				
Immune-related AEs	Toxicity Grade or Conditions (CTCAEv4.03)	Action Taken to Pembrolizumab	irAE Management with Corticosteroid and/or Other Therapies	Monitor and Follow-up
Pneumonitis	Grade 2	Withhold	
 
Administer corticosteroids (initial dose of 1-2mg/kg prednisone or equivalent) followed by taper
 
	
 
Monitor subjects for signs and symptoms of pneumonitis
 
Evaluate subjects with suspected pneumonitis with radiographic imaging and initiate corticosteroid treatment
 
Add prophylactic antibiotics for opportunistic infections
 

	Grade 3 or 4, or recurrent Grade 2	Permanently discontinue		
Diarrhea / Colitis	Grade 2 or 3	Withhold	
 
Administer corticosteroids (initial dose of 1-2mg/kg prednisone or equivalent) followed by taper
 
	
 
Monitor subjects for signs and symptoms of enterocolitis (ie diarrhea, abdominal pain, blood or mucus in stool with or without fever) and of bowel perforation (ie peritoneal signs and ileus).
 
Subjects with <math>\geq</math> Grade 2 diarrhea suspecting colitis should consider GI consultation and performing endoscopy to rule out colitis.
 
Subjects with diarrhea/colitis should be advised to drink liberal quantities of clear fluids. If sufficient oral fluid intake is not feasible, fluid and electrolytes should be substituted via IV infusion.
 

	Grade 4	Permanently discontinue		
AST / ALT Elevation or Increased Bilirubin	Grade 2	Withhold	
 
Administer corticosteroids (initial dose of 0.5- 1 mg/kg prednisone or equivalent) followed by taper
 
	
 
Monitor with liver function tests (consider weekly or more frequently until liver enzyme value returned to baseline or is stable)
 

	Grade 3 or 4	Permanently discontinue	
 
Administer corticosteroids (initial dose of 1-2mg/kg prednisone or equivalent) followed by taper
 
	

Type 1 diabetes Mellitus (T1DM) or Hyperglycemia	Newly onset T1DM or Grade 3 or 4 hyperglycemia associated with evidence of $\beta$ -cell failure	Withhold	
 
Initiate insulin replacement therapy for subjects with T1DM
 
Administer anti-hyperglycemic in subjects with hyperglycemia
 
	
 
Monitor subjects for hyperglycemia or other signs and symptoms of diabetes.
 

Hypophysitis	Grade 2	Withhold	
 
Administer corticosteroids and initiate hormonal replacements as clinically indicated.
 
	
 
Monitor for signs and symptoms of hypophysitis (including hypopituitarism and adrenal insufficiency)
 

	Grade 3 or 4	Withhold or Permanently discontinue		
Hyperthyroidism	Grade 2	Continue	
 
Treat with non-selective beta-blockers (e.g. propranolol) or thionamides as appropriate
 
	
 
Monitor for signs and symptoms of thyroid disorders.
 

	Grade 3 or 4	Withhold or Permanently discontinue		
Hypothyroidism	Grade 2-4	Continue	
 
Initiate thyroid replacement hormones (e.g. levothyroxine or liothyroinine) per standard of care
 
	
 
Monitor for signs and symptoms of thyroid disorders.
 

Nephritis and Renal Dysfunction	Grade 2	Withhold	
 
Administer corticosteroids (prednisone 1-2 mg/kg or equivalent) followed by taper.
 
	
 
Monitor changes of renal function
 

	Grade 3 or 4	Permanently discontinue		
All Other immune-related AEs	Grade 3, or intolerable/persistent Grade 2	Withhold	
 
Based on severity of AE administer corticosteroids
 
	
 
Ensure adequate evaluation to confirm etiology or exclude other causes
 

	Grade 4 or recurrent Grade 3	Permanently discontinue		

**NOTES:**

- Withhold or permanently discontinue pembrolizumab is at the discretion of the Investigator or treating physician.
- For subjects with Grade 3 or 4 immune-related endocrinopathy where withhold of pembrolizumab is required, pembrolizumab may be resumed when AE resolves to  $\leq$  Grade 2 and is controlled with hormonal replacement therapy or achieved metabolic control (in case of T1DM).

Pembrolizumab may cause severe or life threatening infusion-reactions including severe hypersensitivity or anaphylaxis. Signs and symptoms usually develop during or shortly after drug infusion and generally resolve completely within 24 hours of completion of infusion. Dose modification and toxicity management guidelines on pembrolizumab associated infusion reactions are provided in **Table 2**.

**Table 2. Infusion Reaction Treatment Guidelines for Pembrolizumab**

NCI CTCAE Grade	Treatment	Premedication at Subsequent Dosing
Grade 1 Mild reaction; infusion interruption not indicated; intervention not indicated	Increase monitoring of vital signs as medically indicated until the subject is deemed medically stable in the opinion of the investigator.	None
Grade 2 Requires therapy or infusion interruption but responds promptly to symptomatic treatment (eg, antihistamines, NSAIDS, narcotics, IV fluids); prophylactic medications indicated for $\leq$ 24 hrs	
Stop Infusion.            Additional appropriate medical therapy may include but is not limited to:
 
 
IV fluids
 
Antihistamines
 
NSAIDS
 
Acetaminophen
 
Narcotics
 
 
Increase monitoring of vital signs as medically indicated until the subject is deemed medically stable in the opinion of the Investigator.            If symptoms resolve within one hour of stopping drug infusion, the infusion may be restarted at 50% of the original infusion rate (eg, from 100 mL/hr to 50 mL/hr). Otherwise dosing will be held until symptoms resolve and the subject should be premedicated for the next scheduled dose.
 
Subjects who develop Grade 2 toxicity despite adequate premedication should be permanently discontinued from further study drug treatment.
	Subject may be premedicated 1.5h ( $\pm$ 30 minutes) prior to infusion of pembrolizumab with: 
 
Diphenhydramine 50 mg po (or equivalent dose of antihistamine).
 
Acetaminophen 500-1000 mg po (or equivalent dose of analgesic).
 

Grades 3 or 4  Grade 3: Prolonged (ie, not rapidly responsive to symptomatic medication and/or brief interruption of infusion); recurrence of symptoms following initial improvement; hospitalization indicated for other clinical sequelae (eg, renal impairment, pulmonary infiltrates)  Grade 4: Life-threatening; pressor or ventilatory support indicated	
Stop Infusion.            Additional appropriate medical therapy may include but is not limited to:
 
 
Epinephrines**
 
IV fluids
 
Antihistamines
 
NSAIDS
 
Acetaminophen
 
Narcotics
 
Oxygen
 
Pressors
 
Corticosteroids
 
 
Increase monitoring of vital signs as medically indicated until the subject is deemed medically stable in the opinion of the Investigator.            Hospitalization may be indicated.            **In cases of anaphylaxis, epinephrine should be used immediately.  Subject is permanently discontinued from further study drug treatment.
	No subsequent dosing

Appropriate resuscitation equipment should be available at the bedside and a physician readily available during the period of drug administration.

For further information, refer to the Common Terminology Criteria for Adverse Events v4.03 (CTCAE) at <http://ctep.cancer.gov>

In Stage 1, any Grade 3/4 infusion reactions mitigated by these actions and either resolving or decreasing to Grade 1/2, if this mitigation occurs within Cycle 1 and the Grade 3/4 infusion reaction does not recur in Cycle 2, will not be counted towards the total of > 4 or 33% of Grade 3/4 adverse events which require halting the study in Stage 1 for each individual indication. Only Cycle 1 Grade 3/4 infusion reactions not controlled by the above measures (or those which recur in Cycle 2) will be counted towards the total which would halt advancement to Stage 2.

Dose will be managed individually for each study drug.

### **5.2.1.3 Dose Interruptions**

Dosing interruptions are permitted in the case of medical/surgical events or logistical reasons not related to study therapy (eg, elective surgery, unrelated medical events, vacation, and/or holidays). Subjects should be placed back on study therapy within 3 weeks of the scheduled interruption, unless otherwise discussed with the Sponsor. The reason for interruption should be documented in the subject's study record.

### **5.2.2 Timing of Dose Administration**

If Stage 1 proceeds without the need for any dose modification as described in [Section 5.2.1.2.1](#), Imprime PGG will be administered to all subjects at a dose of 4 mg/kg IV over a 2-hour infusion time period on Day 1, Day 8, and Day 15 of each 3-week cycle. Refer to [Appendix 14.1](#) for further details.

If enrollment into an additional cohort in Stage 1 is necessitated based on the dose modification requirements as described in [Section 5.2.1.2.1](#), Imprime PGG will be administered to all subjects in the specified indication at a dose of 2 mg/kg IV over a 2-hour infusion time period on Day 1, Day 8, and Day 15 of each 3-week cycle. Refer to [Appendix 14.1](#) for further details.

Imprime PGG must always be administered first, with a 15-30 minute window before the start of the pembrolizumab infusion.

The pembrolizumab fixed dose of 200 mg will be administered IV over 30 minutes on Day 1 of each 3-week treatment. Sites should make every effort to target infusion timing to be as close to 30 minutes as possible. However, given the variability of infusion pumps from site to site, a window between -5 minutes and +10 minutes is permitted (ie, infusion time is 30 minutes -5 min/+10 min).

### **5.2.3 Trial Blinding/Masking**

Subjects in this study will not be blinded, as all subjects will receive identical treatment.

### **5.3 Randomization or Treatment Allocation**

Neither randomization nor treatment allocation is required in this study, as all subjects will receive identical treatment.

### **5.4 Stratification**

There will be no stratification in this study.

### **5.5 Numbers of Sites and Subjects and Study Duration**

#### **5.5.1 Number of Sites**

It is anticipated there will be approximately 25 sites within the United States. Additional regions, countries, or sites may be added as needed.

Sites that do not enroll subjects within 3 months of site initiation may be closed.

#### **5.5.2 Number of Subjects**

The individual patients in this clinical trial will be referred to as “subjects”.

It is anticipated there will be approximately up to N=94 subjects in total, distributed in the following manner between melanoma and TNBC subjects:

1. Up to N = 41 subjects with melanoma (up to 24 in total in Stage 1 and 17 in Stage 2)
2. Up to N = 53 subjects with TNBC (up to 24 in total in Stage 1 and 29 in Stage 2)

Please refer to [Section 5.9 on Subject Replacement Strategy](#) for further information on the replacement of subjects who do not complete the study.

#### **5.5.3 Study Duration**

Study duration for a subject may last approximately 3 years comprising of the following:

- Screening: Up to 90 days
- Treatment Phase: Up to 2 years
- Survival Follow-up: Up to 1 year

The actual study duration for any individual subject may be shorter or longer than what is listed above, depending on when the subject enrolled during the overall life of the study, and the subject’s individual situation.

### **5.6 Concomitant Medications/Vaccinations (Allowed and Prohibited)**

Subjects should be treated for any concurrent medical conditions at the discretion of the Investigator according to community standards of medical care.

Medications or vaccinations specifically prohibited in the exclusion criteria are not allowed during the ongoing trial. If there is a clinical indication for any medication or vaccination specifically prohibited during the trial, discontinuation from trial therapy or vaccination may be required. The Investigator should discuss any questions regarding this with the Sponsor. The final decision on any supportive therapy or vaccination rests with the Investigator and/or the subject's primary physician. However, the decision to continue the subject on trial therapy or vaccination schedule requires the mutual agreement of the Investigator, the Sponsor, and the subject.

Other than Imprime PGG or pembrolizumab, any medication administered to the subject during any portion of the study after study treatment is initiated on Cycle 1/Day 1 is considered a concomitant medication and must be documented in the electronic Case Report Form (eCRF). This includes all prescription, over-the-counter (OTC), herbal supplements, and IV medications and fluids.

Medications administered during the Screening period should be recorded as prior medications on the eCRF.

### **5.6.1 Acceptable Concomitant Medications**

Most concomitant medications, including pretreatment with anti-emetics, anti-diarrheals, and anti-histamines are permitted and may be administered at the Investigator's discretion.

### **5.6.2 Prohibited Concomitant Medications**

The Sponsor or designee should be notified in advance (or as soon as possible thereafter) of any instances in which prohibited therapies are administered. Continued participation of the subject will be at the discretion of the Sponsor.

Medications or vaccinations contraindicated for use in combination with pembrolizumab include those listed in the exclusion criteria should not be administered. If there is a clinical indication for a medication or vaccination specifically prohibited during the trial, discontinuation from trial therapy or vaccination may be required. The Investigator should discuss any questions regarding this with the local Clinical Monitor.

Following is a list of therapies subjects are prohibited from receiving at any point during this clinical study:

- Antineoplastic systemic chemotherapy or biological therapy
- Immunotherapy not specified in this protocol
- Chemotherapy not specified in this protocol
- Investigational agents other than pembrolizumab or Imprime PGG
- Radiation therapy

Note: Radiation therapy to a symptomatic solitary lesion or to the brain may be considered on an exceptional case-by-case basis after consultation with Sponsor. The subject must have clear measurable disease outside the radiated

field. Administration of palliative radiation therapy will be considered clinical progression for the purposes of determining PFS.

- Live vaccines within 30 days prior to the first dose of trial treatment and while participating in the trial. Examples of live vaccines include, but are not limited to, the following: Measles, mumps, rubella, chicken pox, yellow fever, rabies, BCG, and typhoid (oral) vaccine. Seasonal influenza vaccines for injection are generally killed virus vaccines and are allowed. However, intranasal influenza vaccines (eg, Flu - Mist®) are live attenuated vaccines, and are not allowed.
- Systemic glucocorticoids for any purpose other than to modulate symptoms from an event of clinical interest of suspected immunologic etiology. The use of physiologic doses of corticosteroids may be approved after consultation with the Sponsor.

Note: Inhaled steroids are allowed for management of asthma

In addition, no additional investigational agents are to be administered during the study. In the event a subject develops neutropenia, GCSF administration is allowed (to be administered per ASCO guidelines and/or the site's standard of care).

Subjects who have received palliative radiotherapy for pain will be assessed during the data analysis phase to determine if their data may be assessed with that of other subjects, or if their data should be truncated at the time of receiving the radiotherapy with data extrapolated for all remaining visits as the response assessment may be affected.

There are no prohibited therapies Post-Treatment, however any such therapies must be recorded during the time the subject is being followed for OS.

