9 DATA HANDLING CONVENTIONS

9.1 Premature Withdrawal and Missing Data

For all subjects, all data up to the time of completion of study participation will be included in the analysis, regardless of duration of treatment or follow-up.

Missing data occurs when any requested data is not provided leading to blank field on the collection instrument. These data will be indicated by a dash in the subject listing displays. Answers such as "Not applicable" and "Not evaluable" are not considered to be missing data and should be displayed as such.

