9.3 Imputation of Partial Dates

Partial dates in selected datasets as specified below will be imputed. Imputed partial dates will not be used to derive the study day, duration (e.g., duration of adverse events), or elapsed time variables. However, imputed dates may be used as temporary variables for the purpose of sorting data in the listings. In addition, partial dates may be imputed for ‘slotting’ data to specific study time periods. Imputed dates will not be displayed in the listings.

The partial date will be included in the dataset with the imputed date and a flag variable to indicate the level of imputation. The flag variable can contain the values: blank and 'D'.

Blank: indicates that no imputation is done

D='Day': indicates that the day portion of the date is imputed

Start dates for the new anti-cancer therapy after the study treatment discontinuation will be temporarily imputed in order to define the event and censoring rules for PFS and duration of response. Dates will only be imputed when a month and year are available but the day is missing. The following rules will be used to impute the date when partial start dates are present on the post-treatment new anti-cancer therapy dataset:

Table 1: Rules for Imputation of Partial Dates

Dataset	Date	Missing Element	Rule
Anti-Cancer Therapy	Start Date	day, month, and year	No Imputation for completely missing dates
		day, month	No imputation for missing day and month
		day	If the partial date falls in the same month as the last dose of the study treatment, then assign to earlier of (date of last dose of study treatment+1, last day of month). If the partial date falls in the same month as the subject’s last radiological disease assessment and the subject’s last assessment is PD, then assign to earlier of (date of PD+1, last day of month). If both rules above apply, then assign to the later of the 2 dates. If the partial date falls in the months after the month of last dose of study treatment or last radiological assessment of PD, impute the missing day to the first day of the month.

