11.1 Primary Efficacy Analysis

The primary efficacy endpoint is the overall response rate (ORR), which is defined as the proportion of subjects demonstrating complete response (CR) or partial response (PR) based on RECIST1.1.

The evaluation of response based on RECIST 1.1 will be performed at baseline and then at 6- week intervals beginning at week 6. The best response is the best response recorded from the start of study treatment until the first disease progression based on RECIST1.1 or start of new cancer therapy, whichever occurs earlier. The best response will be determined programmatically based on the investigator's assessment of response at each time point, using the following rules:

Table 1 Best Overall Response When Confirmation of Complete Response and Partial Response is Required

Overall Response First Timepoint	Overall Response Subsequent Timepoint	Best Overall Response
CR	CR	CR
CR	PR	SD, PD or PR ^a
CR	SD	SD provided minimum criteria for SD duration was met, otherwise, PD
CR	PD	SD provided minimum criteria for SD duration was met, otherwise, PD
CR	NE	SD provided minimum criteria for SD duration was met, otherwise, NE
PR	CR	PR
PR	PR	PR
PR	SD	SD
PR	PD	SD provided minimum criteria for SD duration was met, otherwise, PD
PR	NE	SD provided minimum criteria for SD duration was met, otherwise, NE
NE	NE	NE

a: If a CR is truly met at first time point, then any disease seen at a subsequent time point, even disease meeting PR criteria relative to baseline, makes the disease PD at that point (since disease must have reappeared after CR). Best response would depend on whether minimum duration for SD was met. However, sometimes 'CR' may be claimed when subsequent scans suggest small lesions were likely still present and in fact the patient had PR, not CR at the first time point. Under these circumstances, the original CR should be changed to PR and the best response is PR.

CR=complete response; NE=not evaluable; PD=progressive disease; PR=partial response; SD=stable disease.

Note: the minimum criteria for SD is the interval of 5 weeks (35 days).

As further clarification:

- To be assigned CR or PR as the best response, it must be confirmed no less than 4 weeks (28 days) from the time of the initial CR or PR;

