A summary of the assignments for event and censoring dates for PFS are specified in the following Table 3.

Table 2: Assignments for Event and Censoring Dates for PFS Analysis

Situation	Date of Event (PD/Death) or Censoring	Outcome
No (or inadequate) baseline tumor assessments and the subject has not died (if the subject has died follow the rules for death indicated at the bottom of the table)	Date of the first dose	Censored

Situation	Date of Event (PD/Death) or Censoring	Outcome
No adequate post-baseline assessments of CR, PR, SD or PD, and the subject has not died (if the subject has died follow the rules for death indicated at the bottom of the table)	Date of the first dose	Censored
Progression documented before death or without death	Date of assessment of progression	Event
No progression (or death)	Date of last adequate assessment of CR, PR or SD (on or prior to starting new anti-cancer therapy)	Censored
New anti-cancer treatment starting prior to documented disease progression	Date of last adequate assessment of CR, PR or SD (on or prior to starting new anti-cancer therapy)	Censored
Death before assessment of PD or before any adequate assessment of response	Date of death	Event
PD or death after missing one scheduled assessment	Date of PD or death	Event
PD or death after missing two or more scheduled assessments	Date of last adequate assessment of response of CR, PR or SD (prior to the missed assessments)	Censored

The primary analysis of PFS will be based on the radiological assessment, and the sensitivity analysis of PFS will be based on the radiological and clinical assessment. The PFS based on radiological assessment and PFS based on the radiological and clinical assessment will be summarized descriptively using the Kaplan-Meier method for the Evaluable, All Treated and PP populations. The Kaplan-Meier estimate for the median, first and third quartiles will be determined along with 95% confidence intervals (CI). The Brookmeyer-Crowley method will be used for the confidence interval calculation. The Kaplan-Meier estimate of PFS rate at landmark times including but not limited to 3, 6, 9 and 12 months will be summarized. The Kaplan-Meier Plot of PFS will be provided for the Evaluable and All Treated population. Listing of PFS will be provided for the All Treated population.

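### The protocol leaves subjects irradiated for pain to a choice made during data analysis; the SAP has no radiotherapy rule, and its primary PFS omits the protocol's radiotherapy event

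*Protocol*

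**What the plan says.** **Protocol.** Section 5.6.2 prohibits radiation therapy on study, with exceptions case by case after consultation with the sponsor and only where measurable disease lies outside the field. It then makes two statements about analysis.

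- On PFS: "Administration of palliative radiation therapy will be considered clinical progression for the purposes of determining PFS".
- On subjects irradiated for pain: they "will be assessed during the data analysis phase to determine if their data may be assessed with that of other subjects", or their data may be "truncated at the time of receiving the radiotherapy with data extrapolated for all remaining visits as the response assessment may be affected".

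Section 7.3.4 has the investigator assess response and progression by RECIST v1.1. Section 5.2.3 says there is no blinding. Section 9.2 leaves the detailed analysis to a separate SAP.

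**SAP.** The text does not mention radiotherapy, truncation or extrapolation.

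- Section 9.1: "all data up to the time of completion of study participation will be included in the analysis".
- Section 11.1: best response is taken from the start of treatment "until the first disease progression based on RECIST1.1 or start of new cancer therapy, whichever occurs earlier". New cancer therapy is not defined. Clinical progression without radiological confirmation is not a progression event for best response.
- Section 11.2.4: "The primary analysis of PFS will be based on the radiological assessment". A sensitivity version adds clinical progression. The event table has a censoring row headed "New anti-cancer treatment starting prior to documented disease progression".
- Section 11.2.3: DoR borrows the PFS censoring rules of 11.2.4.
- Section 11.3.2: the irRECIST PFS limits its new-therapy censoring to systemic therapy. Sections 11.1 and 11.2.4 carry no such limit.

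**The concern.** For response, the protocol itself states that radiotherapy may affect the assessment, and then postpones the handling to a stage when the outcomes are known. It names no criterion, no decision-maker and no method of extrapolation. Pooling can keep a response first seen or confirmed after irradiation. Truncation can remove one that was not confirmed beforehand, though not one that was. Extrapolation could go either way: carrying an unconfirmed PR forward, for instance, would supply a confirming visit that was never observed.

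Success requires 4 responses among 29 melanoma subjects or 5 among 41 TNBC subjects. At the boundary one subject decides the result.

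For PFS, the protocol's event does not appear in the SAP's primary definition. The same irradiated subject could be an event, be censored, or be followed on to radiological progression, depending on which text the programmer applies.

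**Working it through.** **1. Reading the texts together for best response.**

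- Protocol 5.6.2: case-by-case choice between pooling and truncation with extrapolation.
- SAP 9.1: all data are used, which does not fit truncation or extrapolation.
- SAP 11.1: the window closes at new cancer therapy. A plain reading could include palliative radiotherapy, but nothing says so.
- SAP 9.3 speaks of start dates "when partial start dates are present on the post-treatment new anti-cancer therapy dataset". That rule serves PFS and DoR, so it does not limit 11.1. It does show that the new-therapy data are thought of as post-treatment.

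These give different answers for a subject irradiated on treatment, and no sentence addressed to radiotherapy says which applies.

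**2. Reading the texts together for PFS.**

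| Text applied | Result for a subject irradiated before radiological PD |
|---|---|
| Protocol 5.6.2 | Event (clinical progression) |
| SAP 11.2.4 primary, radiotherapy not new therapy | Followed to radiological PD or death |
| SAP 11.2.4 sensitivity | Event only if recorded as clinical progression; radiotherapy not named |
| SAP 11.2.4, radiotherapy read as new anti-cancer treatment | Censored at last adequate assessment |

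**3. What one response is worth.** Inputs from protocol 9.1.1: 12 subjects in Stage 1, at least 1 response to proceed; 17 more melanoma or 29 more TNBC subjects; reject at r = 4 of n = 29 or r = 5 of n = 41; null 5% for both; alternatives 23% and 21%.

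P(reject) = sum over x1 = 1 to 12 of P(X1 = x1) × P(X2 ≥ r − x1), with X1 ~ Bin(12, p) and X2 ~ Bin(n − 12, p).

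The plan's own figures reproduce:

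- Early termination under the null: 0.95^12 = 0.540 (stated 0.54).
- Type I error: 0.0500 melanoma, 0.0452 TNBC (stated 0.05).
- Power: 0.9019 melanoma, 0.9059 TNBC (stated 90%).

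SAP 5.1 says the Stage 1 interim analysis has been conducted, so only the final count is varied.

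*Truncation as reference, pooling chosen to keep one response.* Add P(Stage 1 passed, total one short of the bar) under the null:

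- Melanoma: 0.0500 + 0.0980 = 0.1480
- TNBC: 0.0452 + 0.0726 = 0.1178

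*Pooling as reference, truncation removes one response.* Subtract P(Stage 1 passed, total exactly at the bar) under the alternative:

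- Melanoma: 0.9019 − 0.0869 = 0.8150
- TNBC: 0.9059 − 0.0531 = 0.8528

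Both calculations assume that every trial at the margin contains one such subject and that the choice always goes the same way. They are limits, not expectations.

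**4. Estimate at the bar (exact 95% CI).** Melanoma: 3/29 = 10.3% (2.2 to 27.4) against 4/29 = 13.8% (3.9 to 31.7). TNBC: 4/41 = 9.8% (2.7 to 23.1) against 5/41 = 12.2% (4.1 to 26.2).

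No PFS effect is quantified; the documents give nothing to base it on.

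**The case against.** The strongest reply is that the SAP is the detailed analysis document and contains no case-by-case step. It uses all data, derives best response by program, requires confirmation of CR and PR, fixes analysis decisions before database freeze (section 1) and reports departures from plan (section 8). Since 11.3.2 says systemic and 11.1 does not, new cancer therapy in 11.1 may already cover radiotherapy.

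This narrows the point. It rules out saying that the SAP provides for an outcome-driven choice. But a deadline is not a rule, and in an open-label trial responses can be known well before freeze. A program still needs to be told whether radiotherapy closes the window. Neither document says that it does, and nothing withdraws the protocol sentence. Reading radiotherapy as new therapy would also censor in PFS what the protocol calls an event.

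On PFS, the protocol labels the event clinical progression, the SAP has a version that counts clinical progression, the protocol bases secondary endpoints on RECIST v1.1, and PFS is descriptive. That stands: the conflict concerns which version carries the protocol's rule, and no hypothesis test depends on it.

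Rarity also stands. Irradiation is exceptional, and a disputed response further requires that it was for pain, that the response was not confirmed beforehand and that the trial sits at the margin.

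**Conclusion.** The point holds as an unresolved analysis rule on the primary endpoint and an unreconciled PFS definition. It should be fixed, but it does not show that the trial's error rates are wrong.

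The size is bounded, not estimated. Type I error is at most 0.148 (melanoma) or 0.118 (TNBC) if truncation is the reference analysis; power is no lower than 0.815 or 0.853 if pooling is. The documents give no radiotherapy rate, so the likely effect cannot be computed and is probably far smaller.

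Three stronger readings are tempting and are not supported:

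- That the trial faces inflated type I error and lost power together. The two limits come from opposite reference analyses. Leaving extrapolation aside, against pooling the choice can only remove responses, and against truncation it can only keep them.
- That the decision to enter Stage 2 is exposed. SAP 5.1 reports the interim as already done.
- That DoR contradicts the protocol. The protocol states no radiotherapy event for DoR. DoR only inherits, through SAP 11.2.3, the doubt over whether radiotherapy is new anti-cancer therapy.

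**What to change.** Before database freeze:

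1. **Best response.** Delete the case-by-case and extrapolation sentence in protocol 5.6.2. State in SAP 11.1 that the start of palliative radiotherapy closes the best-response window as new cancer therapy does. Keep these subjects in the denominator, keep a CR or PR confirmed before radiotherapy, and extrapolate nothing. Say that this limits the all-data rule in SAP 9.1. Because the protocol requires measurable disease outside the field, report ORR with later assessments retained as a sensitivity analysis.
2. **PFS.** Reconcile SAP 11.2.4 with protocol 5.6.2. At minimum, name palliative radiotherapy as an event in the radiological-plus-clinical PFS, with precedence there over the new-therapy censoring row. State which PFS version implements the protocol's rule, and report radiological-only PFS alongside.
3. **DoR.** In SAP 11.2.3, state that the radiotherapy event row does not apply, and whether radiotherapy censors DoR as new anti-cancer therapy. Without this, the new PFS row could carry over through the shared rules.
4. **Listing.** List irradiated subjects with start dates.

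The cost is a short protocol and SAP amendment. Sample size and decision bars do not change. SAP 10.5 lists only post-treatment cancer therapy, so check that on-treatment radiotherapy dates are in the database; the sponsor should know of the cases from the required consultation. ORR or PFS may come out slightly lower.
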